9.5 Critical Structures

The following table outlines the various normal and critical structures. Institutional standards may be used instead.

Standard Name	Description	
GTV	Primary tumor and involved nodes	
CTV_7000	Primary tumor and involved nodes	
PTV_7000	CTV to PTV expansion should be 5 mm minimal margin without IGRT; 3 mm minimal margin with Daily IGRT	
CTV_5600	First Echelon nodal regions	
PTV_5600	CTV to PTV expansion should be 5 mm minimal margin without IGRT; 3 mm minimal margin with Daily IGRT	
CTV_5000	Lower risk nodal regions	
PTV_5000	CTV to PTV expansion should be 5 mm minimal margin without IGRT; 3 mm minimal margin with Daily IGRT	
CTV_5250	Lower risk nodal regions	
PTV_5250	CTV to PTV expansion should be 5 mm minimal margin without IGRT; 3 mm minimal margin with Daily IGRT	
SpinalCord	Spinal Cord	
SpinalCord_05	Planning Risk Volume of 5 mm	

Standard Name	Description
BrainStem	Brainstem
BrainStem_03	Planning Risk Volume of 3 mm
Parotid_L	Left Parotid
Parotid_R	Right Parotid
OralCavity	Oral Cavity
Lips	Lips
Mandible	Mandible
Pharynx	Uninvolved posterior pharyngeal wall plus adjacent constrictor muscles; should not include PTVs
Esophagus	Cervical Esophagus
Larynx	Glottic/Supraglottic Larynx
External	External border of patient used to define Unspecified Tissue
PTV_7000_8mm	Minimum dose (cold spot within PTV1 not including portion of PTV near (<8mm) skin) defined for a point that is 0.03cc in size
NonPTV_7000	Maximum dose (hot spot > 1cc outside the PTVs)

9.6 Documentation Requirements for IMRT Approach

- Pre-treatment Radiation therapy planning CT scan;
- If IGRT is not used, then orthogonal images that localize the isocenter placement of IMRT are required.
- Compliance Criteria

Treatment breaks must be clearly indicated in the treatment record along with the reason(s) for the treatment break(s). Treatment breaks, if necessary, ideally should not exceed 5 treatment days at a time and 10 treatment days total. Treatment breaks should be allowed only for resolution of severe acute toxicity and/or for intercurrent illness and not for social or logistical reasons. Any treatment break(s) exceeding 5 treatment days for reasons other than toxicity/illness will be considered a protocol deviation.

All treatment plans are to be normalized to provide exactly 95% volume coverage of the PTV1 with 70 Gy for patients with unresected disease.

	Per Protocol	Variation Acceptable	Deviation Unacceptable
Total RT dose to PTV1 (to 95% of the PTV)	70 Gy	None	None
Minimum dose ("cold spot" within PTV1, not including portion of PTV near (<8 mm) skin) defined for a point that is 0.03 cc in size	66.5 Gy (equals 95% of prescribed dose)	< 66.5 but > 63 Gy	≤ 63 Gy
Maximum dose ("hot spot" > 1cc) within PTV1	≤ 77 Gy	> 77 but ≤ 82 Gy	> 82 Gy
Maximum dose ("hot spot" > 1cc outside the PTVs)	< 74 Gy	74-77 Gy	> 77 Gy

	Per Protocol	Variation Acceptable	Deviation Unacceptable
Total dose to PTV2 (to 95% of the PTV)	56 Gy	≥ 45 but < 56 Gy	< 45 Gy
Total dose to PTV3 (to 95% of the PTV)	50-52.5 Gy	≥ 40 but < 50 Gy	< 40 Gy
Total RT dose to spinal cord PRV (0.03 cc)	≤ 50 Gy	≥ 50 but ≤ 52 Gy	> 52 Gy
Definition of Spinal cord PRV	Based on case review by Primary Investigator		
Overall RT treatment time	< 47 days	48-51 days (without a medically appropriate indication for delay)	> 52 days (without a medically appropriate indication for delay).
Non-Medically Indicated Treatment Interruptions	0-2	2-4	> 4

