Missed treatments due to holidays or logistic reasons can be compensated for by delivering an additional BID treatment during the week, OR treating on the Saturday or Sunday of that week, OR adding to the end of treatment.

The primary tumor and involved nodes (CTV1) will typically consist of a 0.5-1.5 cm expansion of the gross tumor volume (GTV) to cover potential local invasion and will be prescribed 2 Gy/fraction, total 70 Gy. Non-uniform or larger expansions to encompass high-risk anatomical compartments may be necessary.

High-risk subclinical disease sites, which include possible local subclinical infiltration at the primary site (primary site CTV2) and first echelon nodes, which are not clinically or radiographically involved (nodal CTV2), should be expanded by 3-5 mm to create PTV2. PTV2 should receive 2 Gy/fraction to a total dose of 60 Gy.

Lower-risk targets (PTV3) (such as neck nodal levels which are not first echelon nodes and are not adjacent to levels containing grossly involved nodes) should receive 44 Gy in 2 Gy fractions.

Either of two options is acceptable for treatment of the low neck. One option is to treat with isocentric matching AP or AP-PA fields with larynx block, matched to the inferior margin of the IMRT portals just above the arytenoids. The dose will be 2 Gy per fraction prescribed to 3 cm depth to a total dose of 44 Gy in 22 daily fractions. Whole-neck IMRT is also allowed as an alternative approach. Involved low neck nodes will receive at least 60 Gy in 30 fractions. This can be achieved by either boosting the low neck field with an additional 16 Gy in 8 fractions, by an AP or AP-PA fields, or by planning the whole neck using IMRT. In cases of gross involvement of the vallecula or low neck, whole-neck IMRT should be considered. Whole-neck IMRT may be preferable if level VI is considered to be at risk due to gross involvement of level IV nodes.

All plans must be normalized such that 95% of the volume of the PTV1 is covered with prescription dose of 70 Gy. Additionally:

- At 1 cc PTV1 volume on the DVH curve, the dose should not be > 110% of the prescribed dose.
- At a volume of 0.03 cc within the PTV1 volume on the DVH curve, the dose should not be < 95% of the prescribed dose.
- For any volume of tissue outside the PTVs that has a size of 1 cc, the dose should not be > 74 Gy for definitive radiation.

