The prescribed radiotherapy dose will be 60-66 Gy in 2 Gy once-daily fraction size 5 days a week. For inverse planning IMRT, the goal is for 95% of the PTV60-66 Gy to receive \geq 2 Gy with a minimum dose (cold spot) of no less than 56 Gy. It is recognized that portions of the PTV60-66 Gy close to the skin may receive significantly less than 56 Gy.

9.4.3 **Definition of Normal Tissues/Organs at Risk (OAR)**

NOTE: Only the parts of the normal tissues/organs at risk outside the PTVs will be considered for dose optimization purposes.

Spinal Cord: The cord begins at the cranial-cervical junction (i.e., the top of the C1 vertebral body). Superior to this is brainstem and inferior to this is cord. The inferior border of the spinal cord for this trial is at approximately T3-4 (i.e., just below the lowest slice level that has PTV on it). The spinal cord shall be defined based on the treatment planning CT scan. In addition, however, a Planning Risk Volume (PRV) spinal cord shall be defined. The PRVcord = cord + 5 mm in each dimension. This is irrespective of whether or not IGRT is used.

Brainstem: The inferior most portion of the brainstem is at the cranial-cervical junction where it meets the spinal cord. For the purposes of this study, the superior most portion of the brainstem is approximately at the level of the top of the posterior clinoid. The brainstem shall be defined based on the treatment planning CT scan. In addition, however, a Planning Risk Volume (PRV) brainstem shall be defined. The PRVbrainstem = brainstem + 3 mm in each dimension.

Lips and Oral Cavity: These should be contoured as 2 separate structures as the goal is to keep the lip dose much lower than the oral cavity dose. The definition of lips is self-explanatory. The oral cavity will be defined as a composite structure consisting of the anterior $\frac{1}{2}$ to $\frac{2}{3}$ of the oral tongue/floor of mouth, buccal mucosa, and palate.

Parotid Glands: Parotid glands will be defined in their entirety (superficial and deep lobes) based on the treatment planning CT scan. Parotid gland volume may include portions of any of the CTVs if the primary or nodal volumes involved or closely approached the parotid, although they can overlap the PTVs.

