9.4.4 IMRT Dose Constraints to Normal Structures

Spinal Cord: The PRVcord (as defined in Section 9.4.3) should not exceed 48 Gy to any volume in excess of 0.03 cc (approximately 3 mm x 3 mm x 3 mm). The spinal cord PRV should not exceed 50 Gy to any volume in excess of 0.01 cc. In treatment planning, the spinal cord PRV should be given the highest priority.

Brainstem: The PRVbrainstem (as defined in Section 9.4.3) should not exceed 52 Gy to any volume in excess of 0.03 cc (approximately 3 mm x 3 mm x 3 mm). In treatment planning, the PRVbrainstem should be given less priority than the PRVcord but more priority than the other critical structures listed below. Brainstem dose should be kept as low as possible in order to minimize nausea and vomiting especially since patients will be receiving cisplatin, which is highly emetogenic.

Lips: Reduce the dose as much as possible. The mean dose should be < 20 Gy.

Oral Cavity: Reduce the dose as much as possible when not registered as the primary site of disease. The mean dose should be < 30 Gy for the non-involved oral cavity. Efforts should also be made to avoid hot spots (> 60 Gy) within the non-involved oral cavity.

Parotid Glands: In most cases, it will be easier to spare one parotid than the other. The treatment planning goal will be for this individual parotid gland to receive a median dose of < 20 Gy and/or a mean dose of < 26 Gy. Taking into account new data suggesting monotonous improvement in saliva as dose is reduced, without a threshold the objective will be to reduce the mean doses to both parotid glands as much as possible. (Variation Acceptable: 26-30 Gy). For the parotid glands, the mean dose, median dose, and V25 Gy for each gland will be evaluated.

Contralateral or ipsilateral submandibular gland: If contralateral level Ib is not a target, aim to reduce mean contralateral submandibular gland to < 26 Gy. Ipsilateral submandibular gland sparing may also be feasible in certain cases so similar dose constraints are recommended. (Variation Acceptable: 26-30 Gy). For the submandibular glands, the mean dose, median dose, and V25 Gy for each gland will be evaluated.

Oropharynx: Reduce the dose as much as possible. Some recommended (but not mandatory) treatment goals include: 1) No more than 33% of the oropharynx exceeds 50 Gy; 2) Mean dose < 45 Gy; 3) No more than 15% of the Oropharynx exceeds 60 Gy.

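### The Section 9.6 radiotherapy compliance table does not match Section 9 on the cord limit, sequential-plan PTV3 dose and the length of a 35-fraction course

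*Combined protocol and SAP*

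**What the plan says.** **Cord.** Section 9.4.3 defines the planning risk volume: "The PRVcord = cord + 5 mm in each dimension". Section 9.4.4 says this volume "should not exceed 48 Gy to any volume in excess of 0.03 cc", and adds: "The spinal cord PRV should not exceed 50 Gy to any volume in excess of 0.01 cc". It ranks the structure above all others: "In treatment planning, the spinal cord PRV should be given the highest priority". In Section 9.6 the row beginning "Total RT dose to spinal cord PRV (0.03 cc" has three grades: Per Protocol at 50 Gy or less, Variation Acceptable from 50 to 52 Gy with both ends included, and Deviation Unacceptable above 52 Gy.

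**Nodal dose.** For sequential plans, Section 9.1 states that "PTV2 should receive 2 Gy/fraction to a total dose of 60 Gy" and that PTV3 "should receive 44 Gy in 2 Gy fractions". For SIB plans it gives 56 Gy and 50-52.5 Gy. The Section 9.6 table lists only the SIB pair as Per Protocol. Its PTV3 variation band runs from 40 Gy to just under 50 Gy.

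**Time.** Section 9.1 schedules sequential plans as 35 fractions in 7 weeks at 5 per week. Section 9.6 grades overall time as Per Protocol below 47 days, Variation Acceptable at 48-51 days and Deviation Unacceptable above 52 days. The last two carry a qualifier about delay without a medical reason. The table does not say whether the first day counts. Non-medical interruptions are banded 0-2, 2-4 and more than 4.

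**The concern.** A compliance table should give one grade to each course, and a course delivered as prescribed should come out as Per Protocol. Here, someone grading from Section 9.6 alone would pass a cord PRV dose that exceeds the limit in Section 9.4.4. The same person would record a variation for a sequential plan that followed Section 9.1 exactly, and for most uninterrupted 7-week courses. At some values the table gives two grades or none, so two people could grade the same course differently. Section 9.7 describes quality assurance only as regularly scheduled discussions, so no other numeric rule settles these cases. At stake are a safety limit on a critical structure and the credibility of the recorded compliance rates.

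**Working it through.** **1. Cord PRV, read as the dose received by the hottest 0.03 cc.** Inputs: 48 Gy at 0.03 cc and 50 Gy at 0.01 cc (9.4.4); cut-points 50 and 52 Gy at 0.03 cc (9.6).

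| Dose at 0.03 cc | Against 9.4.4 | Grade in 9.6 |
|---|---|---|
| up to 48 Gy | within the 0.03 cc limit | Per Protocol |
| above 48, below 50 Gy | over the 0.03 cc limit | Per Protocol |
| exactly 50 Gy | over the 0.03 cc limit | Per Protocol and Variation Acceptable |
| above 50, up to 52 Gy | over both limits | Variation Acceptable |
| above 52 Gy | over both limits | Deviation Unacceptable |

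The gap is 50 − 48 = 2 Gy at the top of the Per Protocol band and 52 − 48 = 4 Gy at the top of the variation band. If 0.03 cc receives more than 50 Gy, the volume above 50 Gy is at least 0.03 / 0.01 = 3 times what 9.4.4 allows.

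**2. Sequential nodal doses.** PTV3: 22 × 2 = 44 Gy, which reproduces the prescribed figure. It lies between 40 and 50 Gy, so it is graded a variation, 50 − 44 = 6 Gy below the Per Protocol band. PTV2: 60 Gy is not a listed value, but it passes if 56 Gy is a minimum.

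**3. Course length.** The plan's own figures reproduce: 35 / 5 = 7 weeks and 35 × 2 = 70 Gy. The SIB doses also imply 35 fractions (70 / 2 = 35 and 56 / 1.6 = 35). This part therefore applies to any definitive 70 Gy plan at 2 Gy per fraction.

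Assume weekday treatment, no holidays and no missed days. The last fraction falls 34 weekdays after the first, and 34 = 6 × 5 + 4.

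- Monday start: 6 × 7 + 4 = 46 elapsed days, 47 inclusive.
- Tuesday to Friday start: the last 4 weekdays cross a weekend, so 6 × 7 + 6 = 48 elapsed, 49 inclusive.

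| Start | Elapsed days and grade | Inclusive days and grade |
|---|---|---|
| Monday | 46, Per Protocol | 47, no band |
| Tuesday to Friday | 48, variation | 49, variation |

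One of the ten start-day and counting combinations is Per Protocol. If the delay qualifier restricts the 48-51 band to delayed courses, the Tuesday-to-Friday courses fall in no band, since they are not under 47 days either.

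Exactly 47 and exactly 52 days have no band. Two interruptions fall in both 0-2 and 2-4.

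**4. Post-operative courses.** Unbroken courses started Monday to Wednesday, as Section 9.1 asks, take 40-42 inclusive days for 30 fractions and 45 for 33. All are Per Protocol.

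**The case against.** The strongest reply concerns the cord. Section 9.4.4 is a planning constraint in advisory wording, while Section 9.6 scores what was achieved; a tight planning goal with a looser scoring limit is coherent. That stands as a possible intention. But the protocol does not state it, the passing column is headed Per Protocol, and structure and volume are the same in both places.

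On nodal dose, the table may have been written for SIB plans only, which makes this an omission. It carries no such restriction, however, so a sequential plan is graded by it.

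On time, footnote k to the Section 13 schedule permits radiotherapy in week 8. It assigns no compliance grade, so the bands still apply.

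It is also fair that most of the misgrading ends in Variation Acceptable, and that the documents attach no exclusion or replacement to these grades.

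A reader might infer more than the text supports:

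- *That the table abandons the fixed cord PRV.* The row reading "Based on case review by Primary Investigator" sits in a grading table and can mean that each contour is judged by case review. Section 9.4.3 and the Section 9.5 structure list both give 5 mm.
- *That the interruption and time rows contradict each other.* This requires one interruption to equal one missed day, always added at the end. Section 9.1 also allows a second daily fraction or weekend treatment, and the two rows measure different things.
- *That post-operative courses are never affected.* This is true only for unbroken courses started Monday to Wednesday. With two missed days added at the end, 33 + 2 = 35 weekdays, or 47-49 inclusive days.

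**Conclusion.** The table is wrong as written in three places: the cord PRV limit (2 Gy too loose for Per Protocol and 4 Gy for an acceptable variation, relative to 9.4.4), the sequential PTV3 dose (6 Gy below the passing band when given as prescribed), and the time bands (an unbroken 35-fraction course passes only from a Monday start counted as elapsed days). The edge defects at 50 Gy, 47 days, 52 days and two interruptions are drafting slips.

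Correction is desirable rather than essential. It would be a mistake to infer that the trial's results are compromised: Section 16.1.1 keeps all treated patients in the analyses, and no endpoint or sample size depends on these grades. No unbroken course is graded unacceptable on time. Nor do the documents show that any patient's cord was over-treated, since the 9.4.4 limit still governs planning.

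The calendar result assumes weekday treatment without holidays. The number of patients affected is unknown, because the documents give neither the share on 35-fraction or sequential plans nor their start days.

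**What to change.** Edit the Section 9.6 table as follows.

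- **Cord row:** at 0.03 cc, use ≤48 / >48 to ≤50 / >50 Gy, which matches 9.4.4. If the radiotherapy investigators intend 50 Gy for scoring, state that 48 Gy is the planning limit and use ≤50 / >50 to ≤52 / >52 Gy. The choice is clinical and theirs to make.
- **Nodal rows:** add sequential-plan values, PTV2 60 Gy and PTV3 44 Gy.
- **Time row:** define the day count and use contiguous bands in which an unbroken 35-fraction course, up to 49 inclusive days, is Per Protocol. The investigators should set the upper limits.
- **Interruption row:** use 0-2 / 3-4 / >4.

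No new data are needed. The change is an amendment requiring IRB approval (Section 8.5). Section 11.10.4 reports a subject in this study with QT prolongation after a 28 mg loading dose, so Phase 2 dosing has begun and courses already graded may need regrading.

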9.7 RT Quality Assurance Reviews

RT Quality Assurance Reviews will be done with participating radiation oncology investigators with regularly scheduled discussions.

9.7.1 Radiation Therapy / Adverse Events

Grade 3-4 (CTCAE, v. 4.03) therapy-induced mucositis and/or dysphagia, which are enhanced by cisplatin, are expected to develop in about two thirds of patients. Nutritional evaluation prior to the initiation of therapy for a prophylactic gastrostomy (PEG) tube placement is highly recommended. Placement of a feeding tube should be recorded, as should use of a feeding tube during and after treatment (e.g., greater than or less than 50% of nutrition by tube). Other common radiation adverse events include: fatigue, weight loss, regional alopecia, xerostomia, hoarseness, transient ear discomfort, dysgeusia, headaches, loss of appetite, and skin erythema and desquamation within the treatment fields.

Less common long-term treatment adverse events include: hypothyroidism, loss of hearing, chronic swallowing dysfunction requiring permanent feeding tube, and cervical fibrosis. Much less common radiation adverse events include: tissue necrosis, secondary cancer, mandibular osteoradionecrosis (< 5% incidence with attention to the standard dental recommendations), and cervical myelopathy (< 1% with restriction of spinal cord dose to \le 45 Gy).

Summary of possible side effects of radiation therapy to the head and neck:

COMMON, SOME MAY BE SERIOUS

In 100 people receiving radiation therapy, more than 20 and up to 100 may have:

- Sores in the mouth and/or throat which can be painful and make it very difficult to chew and or swallow foods
- Mouth dryness or changes in taste and/or smell that may be permanent
- Thick saliva
- Hoarseness
- Tanning or redness and/or irritation of the skin in the head and neck area being treated with radiation
- Ear pain and/or pressure
- Fatigue
- Weight loss
- Permanent hair loss in the area treated with radiation (face, chin, neck)
- Loss of teeth or cavities in the teeth if strict dental care is not followed and/or hypersensitivity of teeth

OCCASIONAL, SOME MAY BE SERIOUS

In 100 people receiving radiation therapy, from 4 to 20 may have:

- Decrease in function of the thyroid gland that may require you to take thyroid replacement medicine to prevent you from feeling tired or sleepy
- Serious damage to the jawbone, voice box, skin, or other parts of the head and neck that may require a major operation to correct and, rarely, can even be life threatening
- Temporary pain or scarring around nerves in the shoulder that could cause numbness and/or weakness
- Breathing problems
- Difficulty with swallowing and eating for which you might need a long term or permanent feeding tube; possibility of inhaling food and/or liquids into the lungs which could also result in pneumonia. This side effect is more likely for patients receiving radiation and cisplatin (Group 1).
- Serious ear infections and/or hearing loss
- Loss of hearing

10 Study Drug (Cisplatin)

Refer to the package insert for detailed pharmacologic and safety information

10.1 Description

Cisplatin is a standard of care chemotherapeutic agent used to treat a myriad of malignancies, including HNSCC and salivary gland cancers. It works by binding DNA and causing crosslinks and adducts [52].

10.2 Formulation

Each vial contains 10 mg of cisplatin (DDP), 19 mg of sodium chloride, 100 mg of mannitol, and hydrochloric acid for pH adjustment. One vial is reconstituted with 10 mL of sterile water. The pH range will be 3.5 to 4.5. Cisplatin injection also is available from the manufacturer in aqueous solution, each mL containing 1 mg cisplatin and 9 mg NaCl and HCL or NaOH to adjust pH.

10.3 Storage and Stability

Reconstituted solution of cisplatin is stable for 20 hours when stored at 27°C and should be protected from light if not used within 6 hours. The vials and injection should not be refrigerated. Cisplatin has been shown to react with aluminum needles, producing a black precipitate within 30 minutes.

10.4 Administration

Cisplatin is an IV chemotherapeutic agent approved to treat head and neck cancers. Cisplatin will be administered per institution's standard of care practice. Common standard of care practice includes dosing cisplatin at 100mg/m² IV q21 days starting on Day 1 of RT for 2-3 doses or dosing cisplatin at 30-40 mg/m² IV on Monday or Tuesday of each week of RT for 6-7 total doses. Cisplatin will be infused per institutional guidelines. Patients who start on q21 day dosing may switch to weekly dosing if deemed necessary by the treating investigator. Per institutional guidelines, patients should receive vigorous hydration and electrolyte replacement. The use of prophylactic anti-emetics including a 5-HT3 inhibitor and dexamethasone should be used per ASCO Guidelines. A NK1 inhibitor such as aprepitant may be used per institutional guidelines.

10.5 Dose Modifications

Dose modifications of cisplatin will be performed by the treating physician per each institution's standard practice. The following are guidelines to aid in decision-making. Escalation of the cisplatin is not allowed once the dose level has been reduced.

